9.1.10 Pregnancy

In the event a subject becomes pregnant during the study, she should be withdrawn. However, the subject will be encouraged to complete the post-treatment follow-up portion of the study to the extent that study procedures do not interfere with the pregnancy.

In addition, any pregnancies in the partner of a male subject during the study or for 60 days after the last dose should also be recorded.

If the pregnancy occurs at any time during the study and the 60 days of last dose of active study medication, the pregnancy should be reported immediately to the Sponsor, using a pregnancy notification form.

Study subjects will give consent on enrollment that the Investigator will report any pregnancy during the study to the Sponsor and that they will be asked to provide information about her pregnancy, delivery, and the health of her infant until age one month. Payment for all aspects of obstetrical care, child, or related care will be the subject's responsibility.

All reported pregnancies will be followed up to final outcome, using the pregnancy and pregnancy follow-up forms. The outcome, including any premature termination, will be reported to the Sponsor. An evaluation after the birth of the child may also be conducted.

Pregnancy complications must be recorded as adverse event(s). If the infant has a congenital anomaly/birth defect this must be reported and followed up as a serious adverse event.

9.1.11 ECG Procedure

All ECG's throughout this study will be performed as standard triplicate 12-lead ECG's, except the ECG at Screening. ECG's will be recorded after 5 minutes in a supine position. Only the Triplicate ECG's will be recorded at least 1 minute apart from each other, not exceeding a time period of 5 minutes for the completion of all three ECG's.

The Investigator (or designee) will interpret the ECG's by use of an electronic measurement using the following categories: within normal limits, abnormal but not clinically significant, or abnormal with clinical significance. ECG's are performed according to the Table 16-1. The following parameters will be recorded from the subject's ECG trace: heart rate, QT interval, PR interval, QRS interval, R-R interval, and QTcF (corrected).

The Investigator will be responsible for assessing the accuracy of the electronic QTc interval recording using Fridericia correction formula

• Fridericia correction: QTcF = QT ÷ cube root of the R-R interval (where R-R is the duration of the entire cardiac cycle)

When ECGs are to be collected at the same time point as a blood collection, ECGs should be collected first to avoid any artificially increased heart rates due to the blood collection.

ECG measurements are to be collected during screening and on Day -2 before subjects are connected to the ABPM device. Additionally, ECG measurements are taken on Day 4, after ambulatory devices (Holter and ABPM) are removed, and Days 5, 7, 10, 17 and 30.

In some cases, it may be appropriate to repeat abnormal ECGs. If a machine-read QTc value is prolonged, repeat measurements may not be necessary if the Investigator's interpretation determines that the QTc value is in the acceptable range.

9.1.12 Check-in Procedure

All subjects will check in to the clinic in the morning for the In-house Period. The following will be assessed:

- 1. Alcohol breath test.
- 2. Urine drug screen.
- 3. Urine pregnancy test.

Version 4.0_06Apr2018

- 4. Any use of prescription or non-prescription medicine other than the allowed concomitant medications within the last 12 hours.
- 5. Any medical condition that could interfere with glucose metabolism, as judged by the Investigator.

Subjects who fulfill one or more of the stated criteria at check—in, will not be able to continue onto the treatment period. The treatment period will be rescheduled. Each treatment period may be rescheduled no more than twice. After that, the subject will be excluded from the study. Replacement of subjects for the dosing period may be permitted to enroll sufficient subjects into the study after discussion with Sponsor and Investigator.

9.1.13 Standardized Meals

During in-house period, subjects will receive standardized meals. The standardized weight maintaining meals will be provided using estimated BMR× activity factor of 1.5 to determine daily caloric intake.

9.1.14 ABPM

The 24-hour blood pressure will be measured by an ABPM device. A validated, reliable, automated, and accurate monitor will be used with a storage function. Blood pressure measurements will be started overnight on Day -2 to familiarize the subjects with the device. During this period, measurements will be taken every 2 hours until the morning of Day -1.

The baseline assessment period will start in the morning of Day -1 until Day 1. Measurements will be taken hourly up to 14 hours and then 2-hourly until 24 hours.

The post-dose assessment period will start in the morning of Day 1. Measurements will be taken hourly up to 14 hours and then 2-hourly until 24 hours every day (for every 24-hour period), until the morning of Day 4.

Time points stated in the Table 16-1. Adequate cuff size will be documented for each subject, after determination of the patient's non-dominant arm circumference. Subject's bedtime and awakening will be recorded to divide the downloaded data into diurnal and nocturnal values. Depending on available PK and safety data, timepoints for measurements may be adjusted for the following cohorts.

Specifications about the ABPM model will be described in the Operational Manual and ABPM Procedure Manual, as well as detailed instructions of blood pressure frequency, data management and medical review.

9.1.15 Holter Monitoring

24-hour heart rate activity will be continuously recorded with an ambulatory Holter monitoring system (eg, Mortara surveyor central system with or without a central reader). Holter electrodes (12 lead, 3-channel placement) will be placed to the subject's chest and will be attached to a small recording monitor. The Holter monitor will be carried in a

pocket or small pouch. Subject's activities or exercises will be recorded while wearing the monitor.

Specifications about the Holter model will be described in the Operational Manual and Holter Procedure Manual, as well as detailed instructions of data management and medical review.

9.1.16 Pharmacokinetic Assessments and Schedule

Blood for PK analysis of the study drugs will be collected at the time points indicated in the Table 16-1 Schedule of Events and follow the PK sampling schedule Table 9-2. One 2-mL sample per scheduled time point will be collected to provide a minimum of 500 μ L of serum for PK measurements and 500 μ L of serum as a secondary back-up sample. Instructions for sample processing and shipment will be provided in the PK Sample and Shipping Instructions. Pre-dose sampling will be taken within 10 minutes before dosing. The actual time of PK sampling should not deviate from the nominal time by more than \pm 5 minutes during the Inpatient Period, and by more than \pm 1 day for the Outpatient Visits and by more than Follow-up Visit \pm 2 days for the Follow-up Visit. The actual time of dosing, actual sampling dates and times should be recorded.

Table 9-2 PK Sampling Schedule

		Pre-dose
Inpatient Period	D 1	4 h
	Day 1	8 h
		12 h
	Doy 2	24 h
	Day 2	36 h
	Day 3	48 h
	Day 4	72 h
	Day 5	96 h
	Day 7	144 h
Outnotiont Visit	Day 10 (±1)	216 h
Outpatient Visit	Day 17 (±1)	384 h
Follow-up Visit	Day 30 (±2)	696 h

[•] Date and time for dosing and PK sampling should be recorded

PK sampling times may be adjusted between the cohorts in case available PK data show that any other times would be more beneficial.

9.1.17 Pharmacodynamic Assessments and Schedule

Blood for PD analyses will be collected at the time points indicated in the Table 16-1 and follow the PD sampling schedule in Table 9-3. Sampling for insulin, C-peptide, GCG, GLP-1, GIP and amino acids will follow the PK sampling schedule, including PK sampling windows. PK sampling windows will apply for all other PD samples as well. Instructions for sample processing and shipment will be provided in the laboratory manual. Pre-dose sampling on Day 1 will be taken within 10 minutes before dosing.

Table 9-3 PD Sampling Schedule

			Leptin, Lipid panel (incl. FFA), CRP	FPG	Insulin, C-peptide, GCG, GLP-1, GIP	Amino acids
	Day -1			X		
		Pre-dose	X	X	X	X
	D 1	4 h			X	X
	Day 1	8 h			X	X
		12 h			X	X
Inpatient	D 2	24 h		X	X	X
Period	Day 2	36 h			X	X
	Day 3	48 h	X	X	X	X
	Day 4	72 h		X	X	X
	Day 5	96 h		X	X	X
	Day 6	120 h		X		
	Day 7	144 h	X	X	X	X
Outpatient	Day 10 (± 1)	216 h		X	X	X
Visit	Day 17 (± 1)	384 h	X	X	X	X
Follow-up Visit	Day 30 (± 2)	696 h		X	X	х

Date and time for dosing and PD sampling should be recorded, D1 blood collection time "pre-dose" should be noted as "pre-dose"

9.1.18 Immunogenicity Assessments

Blood samples will be acquired to determine ADAbs, nAbs and anti-PEG prior to the treatment, on Day 17, and at the Follow-up Visit. One 12-mL sample per scheduled time point will be collected to provide a minimum of 6 mL serum for the 3 anti-assays.

The serum will be split to provide for the following:

A minimum of 1.5 mL of serum for the ADAbs measurements and 0.5 mL of serum as a secondary back-up sample.

A minimum of 1.5 mL of serum for the nAbs measurements and 0.5 mL of serum as a secondary back-up sample.

A minimum of 1.0 mL of serum for the ant-PEG measurements and 0.5 mL of serum as a secondary back-up sample

Instructions for sample processing and shipment will be provided in the PK/Immunogenicity Sample and Shipping Instructions.

9.1.19 Tolerability Assessments

After injection of the study drug, the injection site will be marked with a pen. Assessment of study drug injection site will be performed pre-dose, at 4 and 12-hour post-dose on Day 1 and then daily from Day 2 to Day 7 (a window of ± 15 minutes is allowed).

The local reaction from the injection site, the insertion site, and the adhesive will be evaluated quantitatively using a Draize scale or similar scale. If an injection site reaction like pain on palpation, itching, erythema, edema, induration is observed, it must be recorded as an AE and then will be evaluated using the following scale:

Erythema will be evaluated as follows:

- 0 No erythema
- 1 Very slight erythema (barely perceptible)
- 2 Well-defined erythema
- 3 Moderate to severe erythema
- 4 Severe erythema (beet redness) to slight eschar formations (injuries in depth)

Edema will be evaluated as follows:

- 0 − No edema
- 1 Very slight edema (barely perceptible)
- 2 Slight edema (edges of area well defined by definite raising)
- 3 Moderate edema (raised approximately 1 mm)

• 4 – Severe edema (raised more than 1 mm and extending beyond the area of exposure)

For the irritation assessment, all irritation events will be documented as AEs. The diameter of the affected area will be measured with a paper measuring tape in centimeter (cm) and the condition of the injection site will be recorded. Digital photography will be used to document all positive injection site reactions. In case of clinically significant injection site reactions, subjects may undergo a dermatological consultation and/or cutaneous biopsies for further histological examination of the injection site reaction. Biopsies will be performed using a 4-mm punch biopsy centered on the injection site. The biopsy area will be anesthetized with lidocaine prior to the biopsy. Wound closure will be performed with Steristrips. If stitches are necessary to close the punch area, they will be removed approximately 2 weeks later. The time between injection and biopsy will be recorded. Microscopic and histological examination of the punch biopsies will be performed at a qualified lab.

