Subjects will continue to stay in-house for safety evaluations, PK and PD assessments. They will be released from the CRU in the morning of Day 7 and will return for two outpatient visits on Day 10 and 17.

Outpatient Visits:

Subjects will return to the CRU on Days $10 (\pm 1)$ and $17 (\pm 1)$ for two outpatient visits. Blood samples for PK and PD analyses will be collected, and additional safety assessments will be performed as stated in the Table 16-1.

Follow-up Visit:

A Follow-up Visit will be performed on Day 30 (\pm 2) for final safety procedures. Please see Table 16-1Schedule of Events for details.

Sampling and Assessment:

Time points for study procedures and sample collection are specified in the Table 16-1.

Safety assessments will occur throughout the duration of the study, including monitoring of adverse events (AEs), clinical laboratory tests (eg, chemistry, hematology, coagulation, amylase, lipase and urinalysis), vital signs measurements (blood pressure, heart rate, respiration rate, and aural temperature), 12-lead electrocardiograms (ECGs), ABPM, Holter ECG monitoring, and physical examinations.

Local tolerability assessments will be performed by injection site inspection at specific time-points.

Immunogenicity samples for assessment of ADAbs, nAbs and anti-PEG will be taken prior to dosing, on Day 17, and at follow-up, as stated in the Table 16-1.

The PK samples will be taken in accordance with the PK sampling schedule in section 9.1.16. Sampling may be adjusted based on the results of the SDRM.

The PD samples will be taken in accordance with the PD sampling schedule in section 9.1.17. Sampling time points may be adjusted based on the results of the SDRM.

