9.1.4 Physical Examination

The baseline physical examination will consist of the following body systems: (1) eyes; (2) ears, nose, throat, neck, thyroid; (3) cardiovascular system; (4) respiratory system; (5) gastrointestinal system, mouth; (6) dermatologic system; (7) extremities; (8) musculoskeletal system; (9) central and peripheral nervous system and (10) lymph nodes.

An abbreviated physical exam (based on symptoms and including examination of cardiovascular, respiratory, and gastrointestinal system) will be performed by the Investigator (or a qualified physician at the CRU) at time points indicated in the Table 16-1. A complete physical examination may be performed in case the subjects have symptoms or at the discretion of the Investigator.

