10.4 Procedures

10.4.1 Collection and Recording of AEs

Collection of all AEs (serious AEs and non-serious AEs) will commence from the time the subject signs the informed consent to participate in the study until the post-treatment follow-up visit. Throughout the in-house treatment period, the Investigator will assess whether any subjective AEs have occurred. In order to avoid bias in eliciting AEs, a non-specific question, such as "How have you been feeling since your last visit?" may be asked. Subjects may report AEs occurring at any other time during the study.

All subjects experiencing AEs, whether considered associated with the use of the study medication or not, must be monitored and given appropriate medical treatment at the discretion and judgement of the Investigator until the symptoms subside and any clinically relevant changes in laboratory values have returned to baseline or until there is a satisfactory explanation for the changes observed. All AEs will be documented in the AE page of the CRF, whether or not the Investigator concludes that the event is related to the drug treatment. The event term, start and stop dates, severity, action taken with study drug and outcome, will be documented, along with the Investigator's opinion of the causal relationship between the event and the study drug.

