10.6 Follow-up of AEs and SAEs

All AEs should be followed up and subjects will be rendered appropriate medical care and treatment at the discretion of the Investigator until resolution or until the Investigator and Sponsor concludes that "further follow-up is not necessary". If the AE has not resolved by the post-treatment follow-up visit, the stop date will be recorded as "ongoing."

All SAEs should be followed up until resolution or permanent outcome of the event or until the Investigator and Sponsor judge that further follow-up is not necessary.

If information is not available at the time of the first report and becomes available later, the Investigator should complete a follow-up SAE form at the earliest possible or provide other written documentation and fax it immediately within 24 hours of receipt of information to the Sponsor or designee. Copies of any relevant data from the hospital notes (e.g., ECGs, laboratory tests, discharge summary, postmortem results) should be sent accordingly.

All other non-serious AEs must be followed until the outcome of the event is "recovering" (for chronic conditions), or "recovered", or until the end of the post-treatment follow-up stated in the protocol, whichever comes first, and until all queries related to these AE's have been resolved.

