12.2 Study Endpoints

The study endpoints or derived parameters used to assess whether the study objectives have been met. The endpoints for this study are shown in Table 12-1. Additional endpoints may be added to the SAP as needed to address the needs of the study.

Table 12-1 Study Endpoints

Primary Endpoints (Safety Endpoints)	Primary Endpoints (Safety Endpoints)	Primary Endpoints	Exploratory Endpoints			
To assess the safety of HM15211	To assess the local tolerability of HM15211	To assess the PK profiles of HM15211	To assess the PD properties of HM15211 compared to placebo			
·Clinical findings on physical examination	·Injection site reaction	•Total AUC, including AUC(0-inf)	·Body weight			
Clinical laboratory abnormalities (including serum amylase, lipase, coagulation, TSH, calcitonin)		·Incremental AUC	·Lipid metabolism (Total cholesterol, LDL, HDL, VLDL, Triglycerides, FFA)			
•Vital signs (BP, respiratory rate, temperature, and HR) measurements		·Cmax	•Glucose metabolism (FPG, Insulin, C- peptide)			
•12-lead ECG parameters (the primary ECG endpoint will be QTcF)		·Tmax	·Incretin secretion (GCG, Leptin, GLP-1, GIP)			
•24-hour ABPM (Mean day- and night time systolic/diastolic BP)		•t _{1/2}	•Inflammatory marker (CRP)			

Primary Endpoints (Safety Endpoints)	Primary Endpoints (Safety Endpoints)	Primary Endpoints	Exploratory Endpoints
•24-hour Holter ECG (HR, HRV (e.g. mean heart rate, difference between day and night HR, mean NN intervals, SDNN)		·CL/F	
·Immunogenicity (ADAbs, nAbs, anti- PEG)		•Vz/F	
·Adverse events		·kel	

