16.0 APPENDIX

Table 16-1 Schedule of Events

ASSESSMENT	SCREEN		IN-HOUSE PERIOD								OUTPA VIS	F/U	
Visit/ Timepoint (Day)	- 28	-2	-1	1	2	3	4	5	6	7	10 (± 1)	17 (± 1)	30 (± 2)
IP Administration				X									
Informed consent	X												
Demography	X												
Medical history	X												
Sequestered in clinic/unit		X	X	X	X	X	X	X	X	X			
Physical examination (PE)	X												X
Abbreviated PE		X								X	X	X	
Hematology, serum chemistry, urinalysis	X		X	X		X				X		X	X
Amylase, Lipase	X		X		X	X	X	X	X		X	X	X
Calcitonin	X												X
Coagulation	X		X			X							
TSH	X												X
HbA1c	X												
Hep B, Hep C, HIV	X												
ADAbs, nAbs & anti-PEG			X									X	X
Pregnancy test (urine)		X									X	X	X
Pregancy test (serum)	X												
FSH if postmenopausal	X												
Urine drug screen & alcohol breath test	Х	X									X	X	X
Weight	X	X	X	X	X	X	X	X	X	X	X	X	X
Height, BMI	X												
Vital signs	X	X	X^1	X^1	X^1	X^1	X ¹	X ¹	X ¹	X ¹	X	X	X
Standardized meals		X	X	X	X	X	X	X	X	X			

ASSESSMENT	SCREEN	IN-HOUSE PERIOD									OUTPA VISI	F/U	
Visit/ Timepoint (Day)	- 28	-2	-1	1	2	3	4	5	6	7	10 (± 1)	17 (± 1)	30 (± 2)
IP Administration				X									
Record concomitant medications	X	X	X	X	X	X	X	X	X	X	X	X	X
Record AE'S	X	X	X	X	X	X	X	X	X	X	X	X	X
Injection site assessment				X^3	X	X	X	X	X	X			
12-lead ECG	X	$X^{2,7}$					$X^{2,7}$	X^7		X^7	X^7	X^7	X^7
Holter monitoring ⁴			X	X	X	X	X						
ABP monitoring ⁴		X	X	X	X	X	X						
PK assessment ⁵				X	X	X	X	X		X	X	X	X
Insulin, C- peptide, glucagon ⁶				X	X	X	X	X		X	X	X	X
GLP-1, GIP, amino acid panel ⁶				X	X	X	X	X		X	X	X	X
FPG	X		X ⁶	X^6	X ⁶	X^6	X^6	X^6	X^6	X^6	X^6	X^6	X ⁶
Lipid panel, incl. FFA	X			X ⁶		X ⁶				X ⁶		X^6	
Leptin ⁶				X		X				X		X	
CRP ⁶	C1.1 1		11.1	X		X		·	1	X	D 1	Х	1

 1 Measurements of blood pressure will be performed twice (morning and evening) on Day -1. On Day 1, measurements will be performed pre-dose and at 4, 8 and 12 hours post-dose, on Day 2 at 24 and 36 hours post-dose, on Day 3 at 48 hours, on Day 4 at 72 hours, on Day 5 at 96 hours, on Day 6 at 120 hours, on Day 7 at 144 hours post-dose with a sampling window of \pm 15 min for each timepoint.

Measurements of pulse rate and respiration rate will be performed at time points together with blood pressure measurements. Pulse rate will be assessed in combination with both, supine and standing blood pressure measurements. Respiration rate will be assessed at time points of supine blood pressure measurements.

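### Graded injection-site inspection, used for a primary endpoint, stops at Day 7 although three later visits exist; adding it there is a cheap, minor improvement

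*Protocol*

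**What the plan says.** Protocol 5.1 lists injection-site reaction among the primary safety endpoints. In Table 12-1 it is the only entry in the column headed "To assess the local tolerability of HM15211". Section 6.2 names the method: "Local tolerability assessments will be performed by injection site inspection at specific time-points".

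Section 9.1.19 sets the time-points. The site is assessed "performed pre-dose, at 4 and 12-hour post-dose on Day 1 and then daily from Day 2 to Day 7". In Table 16-1 the row "Injection site assessment" is marked on Days 1 to 7 only, and footnote 3 repeats the Day 1 times. Subjects leave the unit on the morning of Day 7.

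Section 9.1.19 also requires any reaction that is observed to be recorded as an AE and then graded. The erythema and edema scales go down to changes that can barely be seen. This duty has no Day 7 limit. The site is identified by a pen mark made after the injection.

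After discharge, Table 16-1 has AE recording on Days 10, 17 and 30, an abbreviated physical examination on Days 10 and 17, and a full one on Day 30. Section 9.1.4 describes the shorter examination: "An abbreviated physical exam (based on symptoms and including examination of cardiovascular, respiratory, and gastrointestinal system". A complete examination may be done if there are symptoms or at the investigator's discretion. On AE reporting, 10.4.1 says: "Subjects may report AEs occurring at any other time during the study".

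**The concern.** Up to Day 7, someone is scheduled to look at the site and grade it. From Day 8 on, the same primary endpoint depends on a subject mentioning a reaction or an examiner noticing one. The method of ascertainment therefore changes at discharge, although subjects return to the unit three more times. A faint redness or swelling is what a scheduled look finds and a general question may miss. At stake is a possible under-count of mild late reactions in a primary safety endpoint. In addition, the escalation review, which follows Day 10 (section 4.5), has no graded look at the site later than Day 7.

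**Working it through.** The protocol states no figure on this point, so there is none to reproduce. The check is a count and a comparison of sections.

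**Inputs.** Inspection times come from 9.1.19 and Table 16-1. The hours for Days 7, 10, 17 and 30 (144, 216, 384 and 696 h) come from 9.1.6. Visit windows are ±1 day on Days 10 and 17 and ±2 days on Day 30.

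**1. Count of scheduled inspections.** Day 1 contributes 2 (4 h and 12 h) and Days 2 to 7 contribute 6 (nominally 24, 48, 72, 96, 120 and 144 h). The total is 2 + 6 = 8, the last at 144 h. Sections 9.1.19, the Table 16-1 row and footnote 3 agree, so there is no contradiction.

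**2. What captures a reaction at each stage.**

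| Stage | Hours after dose | Scheduled graded site inspections | Physical examination | AE recording |
|---|---|---|---|---|
| In-house, Days 1–7 | 4 to 144 | 8 | Abbreviated on Day 7 | Yes |
| Day 10 | 216 | 0 | Abbreviated; skin not required, gastrointestinal required | Yes |
| Day 17 | 384 | 0 | Abbreviated; skin not required, gastrointestinal required | Yes |
| Day 30 | 696 | 0 | Full; 9.1.4 lists skin for the baseline examination, presumably the same here | Yes |

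So late capture exists at every visit, but none of it is a scheduled graded look at the site.

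**3. Is the Grade 2 stopping rule affected?** Section 6.4.1 stops escalation for a related Grade 2 event lasting more than 7 days (168 h). To meet that duration by the Day 10 visit, the event must have begun before 216 − 168 = 48 h. Across the visit window the limits are 192 − 168 = 24 h and 240 − 168 = 72 h. A continuous reaction of that kind would be present at 5 daily inspections through Day 7 (48, 72, 96, 120 and 144 h), or 4 to 6 across the window. It would already be an open, scored AE at discharge. The rule works through the AE record and does not need a Day 10 score.

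**4. Size of any under-count.** With 5 × 6 = 30 active subjects, let p be the share with a new mild late reaction and c the share of those captured without a scheduled look. The expected number missed is 30 × p × (1 − c). The protocol gives neither p nor c. With p assumed at 10%, purely for illustration, 3.0 reactions are expected: c = 1 misses none, c = 0.5 misses 1.5, and c = 0.25 misses 2.25. The range reaches zero, so no size can be claimed.

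**5. After the change.** Scores at 216, 384 and 696 h give 8 + 3 = 11 post-dose inspections. The intervals after Day 7 are 216 − 144 = 72 h, 384 − 216 = 168 h and 696 − 384 = 312 h.

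**The case against.** The strongest reply is that this is a legitimate choice, stated consistently. The drug is given once. Section 6.3 expects Cmax at about 3 days (72 h), so inspection to 144 h covers about twice that time. Section 4.3 reports no adverse injection-site findings in the animal studies. Late capture is not empty either. AEs are recorded at all three later visits, and 10.4.1 offers a question about how the subject has felt since the last visit. The injection goes into the abdominal wall, and the gastrointestinal examination required on Days 10 and 17 would ordinarily bring the examiner to that region. Reactions already known at discharge stay open under 10.6: "All other non-serious AEs must be followed until the outcome of the event is" recovering or recovered, or until follow-up ends. A reaction captured as an AE counts toward the endpoint.

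All of this stands. It limits the point to mild, unreported late signs and keeps its severity low. It does not turn general capture into a scheduled inspection.

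A reader might also infer three stronger points, which the protocol does not support:

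- **Most of the information is lost.** The uninspected part of follow-up is 696 − 144 = 552 h, or 552/696 = 79% of elapsed time. This would measure lost information only if reactions were equally likely throughout follow-up after a single injection, and nothing in the protocol says so.
- **Antibody results lack a matching site score.** Section 9.1.18 takes samples "to determine ADAbs, nAbs and anti-PEG prior to the treatment, on Day 17, and at the Follow-up Visit", but no objective pairs those results with site findings on the same day.
- **Escalation safety is compromised.** Step 3 of the working shows that the duration rule does not depend on a late score.

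**Conclusion.** The point holds as a minor improvement, not as an error or contradiction. A primary endpoint assessed by scheduled graded inspection loses that inspection at Day 7, and three existing visits pass without it. Reported or visible late reactions are still recorded and scored, and the stopping rules are unaffected. What could be under-counted is limited to mild signs after discharge that the subject does not report and the examiner does not notice. The number cannot be computed and may be zero. No dose decision is shown to change, and the documents give no sign of a known local risk. The conclusion assumes that the Day 10 and 17 examinations are done as 9.1.4 describes and that no other study document schedules a later site inspection.

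**What to change.** In 9.1.19 and in the injection-site row of Table 16-1:

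- Add a scored inspection at the existing Day 10, 17 and 30 visits, using the same erythema and edema scales and each visit's own window.
- Record the location of the injection site at discharge on Day 7, because the pen mark may not last until the later visits.
- In 4.5, have the Day 10 score available to the escalation review as support for the AE record, not as a replacement for it.

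The cost is a few minutes of staff time per visit, one more CRF entry and an edit to the schedule table. No new visit or sample is needed.
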